Official Title of the Study:

Randomized Trial Comparing Intravenous Iron Carboxymaltose, Intravenous Iron Isomaltoside and Oral Iron Sulphate for Postpartum Anemia

NCT Number:

Not yet assigned.

Date of the document:

05/15/2019

RATIONALE

Anemia affects between 20 and 50 % of women in the postpartum period (1). It is associated with several adverse health consequences, such as impaired physical work capacity, deficits in cognitive function and mood, reduced immune function and reduced duration of breastfeeding (1-5). Postpartum anemia has also been shown to be a major risk factor for postpartum depression and to significantly disrupt maternal–infant interactions (1-3).

Iron deficiency is the principal cause of anemia after delivery (1). Oral iron supplementation with ferrous sulfate has been considered the standard of care with blood transfusion reserved for more severe or symptomatic cases (6,7). However, efficacy of oral iron is limited by gastrointestinal side effects, patient non-adherence as well as prolonged time required to treat anemia and replenish body iron stores (7-9). Blood transfusion, on the other hand, is associated with several hazards, including transfusion of the wrong blood type, infection, anaphylaxis and lung injury (7,8,10).

In last decades, modern formulations of intravenous iron have emerged as safe and effective alternatives to oral iron supplementation for iron deficiency anemia management outside pregnancy (11). Several studies have also evaluated efficacy of intravenous iron preparations for treatment of postpartum anemia. Westad et al. reported no significant difference in hemoglobin levels at 4, 8 and 12 weeks postpartum in women receiving intravenous iron sucrose (Venofer®) compared to those receiving oral ferrous sulphate, whereas the total fatigue score was significantly improved in the intravenous iron supplementation group at weeks 4, 8 and 12 (6). In addition, mean serum ferritin value after 4 weeks was significantly higher in the iron sucrose group. Several other authors came to similar conclusion, intravenous iron sucrose and oral ferrous sulphate were both effective in correcting peripartum anemia, although intravenous iron restored stores faster than oral iron (7,12-14).

In the last decade, two new intravenous iron compounds have been registered for clinical use: ferric carboxymaltose (Iroprem®) and iron isomaltoside (Monofer®) (15-18). These treatments were designed to be administered in large doses by rapid intravenous injection. They have been demonstrated to be more efficacious than intravenous iron sucrose in patients with inflammatory bowel disease and in patients with chronic kidney disease (19-21). In the postpartum period, ferric carboxymaltose has been compared to oral iron supplements in four randomized trials. All reported a faster rise in hemoglobin levels compared to oral ferrous

sulphate (15,16,22,23). Pfenninger et al. compared efficacy of intravenous ferric carboxymaltose with iron sucrose for the treatment of postpartum anemia in a retrospective cohort study. Both drugs offered rapid normalization of hemoglobin levels after delivery with no difference in mean daily hemoglobin increase between the groups up to 8 days after treatment (24). Only one randomized study to date compared intravenous ferric carboxylase to intravenous iron sucrose and oral ferrous sulphate for treatment of postpartum anemia. Radhod et al. found a significantly faster rise in hemoglobin and ferritin levels with ferric carboxylase compared to iron sucrose and ferrous sulphate in Indian women presenting with anemia after delivery (25). This study, like most randomized trials on efficacy of various iron treatments, focused solely on hematological biomarkers. However, iron deficiency, even without anemia, contributes significantly to fatigue experienced by women in the puerperium, and these women may benefit from iron supplementation as well (1,16,26). Data on patient reported outcomes associated with different iron treatments are, therefore, very much needed. Holm et al. compared the effects of single-dose intravenous iron isomaltoside to oral iron supplementation on physical fatigue in women after postpartum haemorrhage (17,18). They found significant reduction in fatigue within 12 weeks postpartum in women who received iron isomaltoside (16). Iron isomaltoside treatment was also associated with improved haematological and iron parameters compared to oral ferrous sulfate (17,18).

No study to date, however, compared efficacy of iron carboxymaltose to iron isomaltoside for treatment of postpartum anemia. The only head-to-head comparison between these two compounds merely examined economic aspects of each treatment, showing potential reduction of costs associated with the use of iron isomaltoside vs. iron carboxymaltose (27).

OBJECTIVE

The objective of the study is to compare efficacy of intravenous iron carboxymaltose to intravenous iron isomaltoside and oral iron sulphate for treatment of postpartum anemia.

METHODS

Single-center, randomized, open-label trial.

Inclusion criteria

Postpartum patients with a hemoglobin level between 70 g/L and 100 g/L within 48 hours after delivery.

Exclusion criteria

- Contraindications for any of the study drugs.
- Anemia due to causes other than iron deficiency.
- Signs of systemic infection.
- Renal or hepatic dysfunction.
- Depression during pregnancy or pre-existing depressive disorders.

After signed informed consent patients will be allocated randomly in a 1:1:1 fashion into one of three groups:

1. Iron carboxymaltose group. Total dose of intravenous ferric carboxymaltose (Iroprem®) needed to correct anemia and replenish iron stores will be calculated using the Ganzoni formula (28) modified to include adjustment for baseline iron status: prepregnancy weight in kilograms X (15–baseline Hb) X 2.4 + 500. Fifteen is the target Hb in g/dL, 2.4 is a unit less conversion constant and 500 is the target iron stores in mg. The maximal dose administered in a single day will not exceed 15 mg/kg (current weight) or 1000 mg (for participants with body weight > 67 kg). If total calculated dose will exceed 15 mg/kg or 1000 mg, subsequent doses will be administered weekly until the total calculated dose will be reached.
2. Iron isomaltoside group. Total dose of intravenous iron isomaltoside (Monofer®) needed to correct anemia and replenish iron stores will be calculated as described above. The maximal dose administered in a single day will not exceed 20 mg/kg (current weight) or 1500 mg (for participants with body weight > 75 kg). If total calculated dose will exceed 20 mg/kg or 1500 mg, subsequent doses will be administered weekly until the total calculated dose will be reached.
3. Iron sulphate group. Participants will receive oral ferrous sulphate (Tardyfer®) 160 mg daily for 6 weeks with instruction to take two tablets by mouth once daily 1 hour before meal. They will receive no additional iron supplementation.

We will monitor blood pressure and record adverse events in all patients before and after administration of IV iron and ask all patients to report any untoward medical event at its onset.

Outcomes

Primary outcome

- Multidimensional Fatigue Inventory (MFI) score at 6 weeks postpartum. The MFI evaluates five dimensions of fatigue: general fatigue, physical fatigue, reduced activity, reduced motivation, and mental fatigue, and consists of 20 statements for which the participant indicates, on a five-point scale, the extent to which the particular statement applies with regard to aspects of fatigue experienced during the previous days. Higher scores indicate a higher degree of fatigue.

Secondary outcomes

- Edinburgh Postnatal Depression Scale (EPDS) score at 6 weeks postpartum. EPDA is a 10-item questionnaire which evaluates different depression symptoms, such as guilt feeling, sleep disturbance, low energy, anhedonia, and suicidal ideation. Overall assessment is done by total score, which is determined by adding together the scores for each of the 10 items. Higher scores indicate more depressive symptoms.
- Mean hemoglobin level at 6 weeks postpartum.
- Proportion of participants with hemoglobin level > 120 g/L at 6 weeks postpartum.
- Proportion of participants with ferritin level > 50 mcg/L at 6 weeks postpartum.
- Mean reticulocyte count at 6 weeks postpartum.
- Mean ferritin level at 6 weeks postpartum.
- Mean transferrin level at 6 weeks postpartum.
- Costs of treatments
- Compliance with oral ferrous sulphate treatment
- Side effects of all three study treatments in mothers (e.g. constipation, headache, infusion site burning) and infants (e.g. constipation, erythema, diarrhea, abdominal pain, upper respiratory tract infection)

Statistical analysis

The planned sample size of 100 patients per group was based on a 80% power to detect non-inferiority using a margin of 5 (half the estimated clinically relevant difference in MFI), an α of 0.01, and expected standard deviation (SD) of 10, with a 20 % dropout rate.

All data will be analyzed according to a pre-established statistical plan. Statistical analyses will be performed with SPSS software (version 24.0; IBM Corporation, Armonk, New York). Data will be entered as numerical or categorical, as appropriate. Shapiro-Wilk test will be used to assess normality of distribution. Parametric statistics will be carried out for normally distributed variables; for non-normal distribution, we will use nonparametric statistics. Data with normal distribution will be described using minimum, maximum, and mean with standard deviation. Data with non-normal distribution will be described using minimum, maximum, median, and interquartile range (IQR). Comparisons will be carried out between the study groups using independent Student's t test or Mann-Whitney U test for continuous and with Chi-square test for categorical variables.

REFERENCES

8. Cook JD. Diagnosis and management of iron-deficiency anaemia. *Best Pract Res Clin Haematol.* 2005;18(2): 319-32

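### The only scheduled adverse-event recording is tied to IV iron, so the three-arm comparison of side effects is open to bias from unequal ascertainment

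*Combined protocol and SAP*

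**What the plan says.** The combined protocol and SAP gives adverse-event collection one sentence, placed in METHODS after the description of the oral group. It sets out two routes.

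- **Scheduled:** "We will monitor blood pressure and record adverse events in all patients before and after administration of IV iron".
- **Unscheduled:** staff will "ask all patients to report any untoward medical event at its onset".

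The last item under Secondary outcomes is "Side effects of all three study treatments in mothers (e.g. constipation, headache, infusion site burning) and infants". It has no time point, form or visit, whereas the fatigue, depression and laboratory outcomes are all fixed at 6 weeks.

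The treatment schedules differ. In both IV groups, when the calculated total exceeds the single-day cap, "subsequent doses will be administered weekly until the total calculated dose will be reached". The oral group takes iron "160 mg daily for 6 weeks with instruction to take two tablets by mouth once daily 1 hour before meal" and receives no other iron. The design is described as "Single-center, randomized, open-label trial". Under Statistical analysis, categorical variables are compared between groups by chi-square, with no provision for differences in how events were collected.

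**The concern.** The first route is timed by an event that oral-arm women never experience. The phrase covering all patients cannot change that. Followed as written, the plan gives the two IV arms active recording plus self-report and the oral arm self-report alone. No solicited assessment common to the three arms is specified, and for infants the only route that clearly applies is the mother's own report.

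The extra recording is also confined to infusion days, at the start of follow-up, while oral exposure lasts the full 6 weeks.

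The RATIONALE says that "efficacy of oral iron is limited by gastrointestinal side effects", so tolerability of oral against IV iron is a comparison readers will look for. If oral-arm events are found less completely, oral iron will look closer to IV iron than it is. Because treatment is known to everyone, readier reporting by women taking daily tablets could push the other way. Data not solicited during follow-up cannot be recovered at analysis.

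**Working it through.** The plan states no figure for side effects, so there is none to reproduce. The check has two parts: how many scheduled recording occasions each arm gets, and what that imbalance could do under assumed rates.

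**1. Recording occasions, from the protocol's dose rules**

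Inputs from METHODS:

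- Total dose (mg) = prepregnancy weight × (15 − Hb in g/dL) × 2.4 + 500.
- Single-day cap on current weight: 15 mg/kg up to 1000 mg (carboxymaltose); 20 mg/kg up to 1500 mg (isomaltoside).
- Hb 7 to 10 g/dL at entry.

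Assumed: prepregnancy weight 50 to 90 kg, and current weight 5 kg higher (10 kg higher in brackets in the table).

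Infusion days = total dose ÷ cap, rounded up. Examples with +5 kg:

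- 65 kg, Hb 8.5: 65 × 6.5 × 2.4 + 500 = 1514 mg. Caps are 1000 and 20 × 70 = 1400 mg, giving 2 days in each IV arm.
- 80 kg, Hb 7: 80 × 8 × 2.4 + 500 = 2036 mg. Caps are 1000 and 1500 mg, giving 3 days against 2.

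On a grid of 9 weights (5 kg steps) by 7 Hb values (0.5 steps), 63 cells:

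| Arm | 0 days | 1 day | 2 days | 3 days |
|---|---|---|---|---|
| Carboxymaltose | 0 | 0 | 57 (57) | 6 (6) |
| Isomaltoside | 0 | 11 (16) | 52 (47) | 0 (0) |
| Oral | 63 | 0 | 0 | 0 |

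The IV arms have equal numbers of days in 46 (41) cells, and carboxymaltose has one more in 17 (22). With weekly dosing, the last infusion falls at week 0, 1 or 2. Cells are not weighted by how common such women are.

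**2. Illustrative effect on the comparison (all rates assumed)**

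True constipation risk is 20% oral and 10% IV. Onset is uniform over 6 weeks. A fraction v of events is volunteered. In the IV arms, every event up to the last infusion is elicited.

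- Observed oral = 20% × v.
- Observed IV = 10% × [f + (1 − f) × v], where f = (infusion days − 1)/6.

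For v = 0.5 and 2 days: f = 1/6; IV = 10% × (0.1667 + 0.8333 × 0.5) = 5.83%; oral = 10.0%; ratio 10.0/5.83 = 1.71.

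| v | Oral % | IV %, 1 / 2 / 3 days | Ratio, 1 / 2 / 3 days (true 2.0) |
|---|---|---|---|
| 0.3 | 6.0 | 3.00 / 4.17 / 5.33 | 2.0 / 1.44 / 1.13 |
| 0.5 | 10.0 | 5.00 / 5.83 / 6.67 | 2.0 / 1.71 / 1.50 |
| 0.7 | 14.0 | 7.00 / 7.50 / 8.00 | 2.0 / 1.87 / 1.75 |
| 0.9 | 18.0 | 9.00 / 9.17 / 9.33 | 2.0 / 1.96 / 1.93 |

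At v = 0.5, the true difference of 10 points is seen as 5.0, 4.2 or 3.3 points. The first 5 points lost are under-reporting common to all arms. Unequal collection accounts for the other 0, 0.8 or 1.7.

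**3. Equal true rates**

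With 15% in every arm and v = 0.5, oral shows 7.5%. IV shows 15% × 0.5833 = 8.75% with 2 days and 15% × 0.6667 = 10.0% with 3, a gap made by collection alone.

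For 8.75% against 7.5% with 100 per arm, the pooled standard error is √(0.08125 × 0.91875 × 0.02) = 0.0386, nearly the same as the unpooled one. The chance of a two-sided 5% result is Φ((0.0125 − 1.96 × 0.0386)/0.0386) + Φ((−0.0125 − 1.96 × 0.0386)/0.0386), about 0.06.

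**The case against.** The strongest counter-reading is that the scheduled recording is infusion-safety monitoring. It is paired with blood pressure, and nothing says that staff will ask about constipation or infant symptoms on those days. On that reading, such events are collected alike in all arms, by self-report, and what remains is under-specification. The full elicitation assumed in the illustration would then overstate the effect. This has force for constipation, but it does not remove the problem. The text refers to adverse events without restricting them to infusion reactions, and headache, one of the plan's own examples, would be actively recorded only in the IV arms.

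Second, oral-arm women are assessed at 6 weeks, and their compliance is an outcome, so side effects may well be asked about then. That is plausible, but the document does not say so.

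Third, the size is modest in the usual case. Three infusion days occur in only 6 of 63 grid cells, in one arm. A single infusion gives no distortion under the model. Two days at half volunteered costs 0.8 points. All of this stands.

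Fourth, side effects are the last-listed secondary outcome in a trial whose objective is efficacy, with no power claim attached. This limits the importance of the point but does not answer it.

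**Conclusion.** The concern holds. As written, the plan gives unequal ascertainment of a listed secondary outcome: at least one scheduled recording occasion in each IV arm (usually two under the assumed weights) and none in the oral arm. The oral arm is not without data, because onset self-report applies to everyone.

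Neither the size nor the direction of the bias can be established from the documents. Under the assumed rates, and with two infusion days, a true ratio of 2.0 would be seen as between 1.44 (30% of events volunteered) and 1.96 (90%). The direction of effect is kept wherever the true rates differ in this example. Differences between the two IV arms in the number of recording occasions are a minor addition. The primary fatigue analysis is untouched. This should be corrected, but it does not threaten the trial's main conclusion. Confidence is medium, because the sentence can be read more narrowly and every rate used is assumed.

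**What to change.** Add to METHODS:

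> At the 6-week assessment, women in all three groups complete the same structured checklist of the maternal and infant symptoms listed under secondary outcomes, covering the whole period since allocation.

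Add to Statistical analysis:

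> The checklist is the main basis for the between-group comparison of side effects. Events self-reported at onset, from all groups and including women lost before week 6, are a supporting analysis. Peri-infusion events, infusion-site symptoms and blood pressure are described for the two IV groups only.

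The existing monitoring sentence should also be reworded so that it is clear which women and which events it covers. Monitoring around infusions stays as it is.

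The cost is one short form at an assessment that already takes place, plus a few sentences of text. The drawback is recall error over 6 weeks. It may differ between arms, because the trial is open-label and oral treatment ends later than IV treatment. Women lost before week 6 will have no checklist (the sample size was set "with a 20 % dropout rate"), which is why the onset reports are kept.

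### Fatigue (MFI) and depression (EPDS) scores are specified only at 6 weeks and compared unadjusted, so the trial gives up precision and cannot describe entry fatigue or dropout on its primary scale

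*Combined protocol and SAP*

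**What the plan says.** Under Outcomes, the primary outcome is the "Multidimensional Fatigue Inventory (MFI) score at 6 weeks postpartum", and the first secondary outcome is the "Edinburgh Postnatal Depression Scale (EPDS) score at 6 weeks postpartum". Neither questionnaire appears at any other time point.

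Under METHODS, the step after eligibility is: "After signed informed consent patients will be allocated randomly in a 1:1:1 fashion into one of three groups". No questionnaire is placed before that step. The pre-treatment information mentioned is hemoglobin, body weight, and blood pressure and adverse events around the infusions. Depression enters only as an exclusion by history.

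Under Statistical analysis: "The planned sample size of 100 patients per group was based on a 80% power to detect non-inferiority", with a margin of 5 MFI points, "an α of 0.01, and expected standard deviation (SD) of 10, with a 20 % dropout rate". Continuous outcomes are compared between groups by t test or Mann-Whitney U test. No covariate, change score or stratified randomization is mentioned.

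**The concern.** Women enter on hemoglobin, but the primary outcome is fatigue. The RATIONALE itself says that iron deficiency contributes to fatigue even without anemia, so hemoglobin is at best a weak proxy for how tired a woman is at entry. Starting fatigue is therefore free to vary between women. Whatever part of it persists to 6 weeks stays in the error term of the primary comparison.

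Three things are at stake:

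- **Precision.** A baseline score used as a covariate would remove that persistent part and narrow the confidence bound that is set against the 5-point margin.
- **Description.** Without an entry score, the report cannot say how fatigued the women were when randomized.
- **Dropout.** The plan expects 20% loss, about 20 of 100 women per arm. Without an entry score, women who return at 6 weeks cannot be compared with those who do not on the scale that matters most.

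The gap cannot be repaired afterwards. The trial is open-label, so a score taken once the woman knows her arm could be influenced by that knowledge.

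**Working it through.** **Inputs from Statistical analysis:** margin 5, SD 10, alpha 0.01, power 80%, dropout 20%, 100 women per group. **Assumptions:** a true difference of 0, a baseline SD of 10, and a baseline-to-6-week correlation r of 0.3, 0.5 or 0.6. The documents give no value for r.

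**1. Reproduce the plan's figure.** With one-sided alpha 0.01 (z = 2.326) and 80% power (z = 0.842):

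n = 2 × 10² × (2.326 + 0.842)² / 5² = 80.3, so 81 evaluable per group.

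For 20% dropout, 81 / 0.8 gives 102 and 81 × 1.2 gives 98. Both agree with 100 per group. Reading alpha as two-sided gives 94 evaluable and 118 (or 113) after dropout, which does not agree. The one-sided reading is used below.

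**2. Unadjusted precision.** 100 less 20% leaves 80 evaluable per arm.

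- SE of the difference = 10 × √(2/80) = 1.58 points.
- Distance from the estimate to the one-sided 1% bound = 2.326 × 1.58 = 3.68 points.
- Power = Φ(5/1.58 − 2.326) = Φ(0.84) = 79.8%.

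The stated 80% therefore holds without any baseline score.

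**3. Chance baseline gap and the part that carries over.** If the baseline SD is also 10, the gap in baseline means between two arms of 80 has the same SE, 1.58 points, and a 95% range of ±1.96 × 1.58 = ±3.1. Only r times that gap is expected to reach the 6-week difference:

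- r = 0.3: 0.3 × 3.1 = ±0.9 points
- r = 0.5: 0.5 × 3.1 = ±1.5 points
- r = 0.6: 0.6 × 3.1 = ±1.9 points

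**4. Effect of ANCOVA.** The residual SD is 10 × √(1 − r²), and the SE, bound and power follow as in step 2.

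| r | Residual SD | SE | One-sided 1% bound | Power at true difference 0 |
|---|---|---|---|---|
| 0 | 10.00 | 1.58 | 3.68 | 80% |
| 0.3 | 9.54 | 1.51 | 3.51 | 84% |
| 0.5 | 8.66 | 1.37 | 3.19 | 91% |
| 0.6 | 8.00 | 1.26 | 2.94 | 95% |

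Put the other way, holding power at 80% would need 93, 77 or 65 women per group after dropout at r = 0.3, 0.5 and 0.6, against 102 unadjusted.

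**5. Why ANCOVA and not a change score.** With equal SDs, the SD of the change is 10 × √(2(1 − r)): 11.83 at r = 0.3, 10.00 at r = 0.5 and 8.94 at r = 0.6. A change score loses precision below r = 0.5 and gains only above it. ANCOVA does not have this drawback. At r = 0 it costs about one degree of freedom out of 158.

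No such calculation can be made for the EPDS, because the documents give no SD or margin for it.

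**The case against.** The strongest reply is that comparing randomized groups on a follow-up score alone is a legitimate design. The planned SD of 10 is applied to the 6-week score unadjusted, so it already contains the variation in starting fatigue, and the confidence interval already allows for chance imbalance. This stands. A reader might infer that the missing baseline biases the comparison or invalidates the power statement. The documents do not support that: allocation is random, and step 2 reproduces the stated power.

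A reader might also set the raw baseline gap against the margin: ±3.1 points, with about an 11% chance per pair of arms of exceeding 2.5 points, half the margin. That overstates the matter, because it would apply only if r were 1. The chance that the carried part exceeds 2.5 points is under 0.001% at r = 0.3, about 0.16% at r = 0.5 and about 0.8% at r = 0.6.

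Nor would a baseline show that two drugs found to be similar had both worked. Fatigue measured just after delivery may fall without treatment, so a fall within an arm is not evidence of drug effect. The oral arm is an active treatment and does not settle that question either.

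The correlation may well be modest. The MFI asks about the preceding days, and women enter on a hemoglobin value from within 48 hours of delivery, so an entry score would partly reflect the delivery itself. This stands and limits the gain. For the EPDS, the depression exclusions probably narrow the starting variation as well.

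Finally, the protocol is brief and lists no baseline dataset at all, and it refers to a pre-established statistical plan. The supportable statement is that a baseline score is not specified; the documents do not show that none will be collected. However, no analysis plan can adjust for a score that was not collected, and the tests actually described use no covariate.

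**Conclusion.** The point holds as a missed gain in precision and a gap in description. It is a cheap improvement and not a flaw in validity.

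The precision gain is about 4, 11 and 15 percentage points of power at r = 0.3, 0.5 and 0.6, with the bound narrowing by 0.17, 0.49 and 0.74 points. It is negligible near r = 0. These figures rest on one-sided alpha 0.01, 80 evaluable women per arm, SD 10, a true difference of 0, and a correlation that has to be assumed.

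The other two losses do not depend on r: fatigue at entry cannot be described, and completers cannot be compared with dropouts on the primary scale.

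**What to change.** Three changes:

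1. Have every woman complete the MFI and EPDS after consent and before her allocation is revealed.
2. Prespecify ANCOVA of the 6-week score on the baseline score for both questionnaires, in place of the unadjusted tests.
3. Report baseline scores by arm, and by whether the 6-week score was obtained.

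The protocol should also state that alpha 0.01 is one-sided, since only that reading agrees with 100 per group.

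The cost is a few lines of protocol text and 30 self-completed items per woman (20 MFI, 10 EPDS) at enrollment, with no extra visit or sample. The downside is a short burden soon after delivery, for a precision gain that may prove modest. The planned sample size need not change: with r unknown, any gain is best kept as reserve.

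### If treatment costs fail the plan's normality check, no mean cost difference is reported, so the result cannot be turned into total spend

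*Combined protocol and SAP*

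**What the plan says.** Under Outcomes, Secondary outcomes, the whole entry is "Costs of treatments". It gives no cost items, unit prices, summary measure or test.

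Statistical analysis has one rule for all continuous variables. First, "Shapiro-Wilk test will be used to assess normality of distribution"; then "for non-normal distribution, we will use nonparametric statistics". Non-normal data are described by their range, median and quartiles, without a mean. Groups are compared by "independent Student's t test or Mann-Whitney U test for continuous" variables. Costs are not exempted. That section refers to a plan fixed in advance, but the document contains no further cost method.

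Two other places bear on cost. The Rationale says the only head-to-head comparison of the two IV drugs was economic and showed "potential reduction of costs associated with the use of iron isomaltoside vs. iron carboxymaltose". Methods gives both IV arms the same total dose, "prepregnancy weight in kilograms X (15–baseline Hb) X 2.4 + 500", but different single-day limits. For carboxymaltose the daily dose "will not exceed 15 mg/kg (current weight) or 1000 mg"; for isomaltoside the limits are 20 mg/kg or 1500 mg. Any remainder is given at weekly intervals, so the number of infusion visits can differ between the arms.

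**The concern.** Total spend is the mean cost per woman times the number treated. A median cannot be scaled up in this way, and Mann-Whitney compares ranks rather than average costs. If costs go down the non-normal branch, the report would hold nothing from which a reader could work out what choosing one drug over the other would cost or save.

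The dosing rules make this more than a formal point. A minority of isomaltoside women can finish in one visit while the typical woman in either IV arm needs two. The saving then sits in a minority, which a median can miss entirely.

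**Working it through.** **The plan's own figure.** No cost figure is stated. The only number used from the sample-size paragraph is 100 per group. It reproduces at one-sided α 0.01: 2 × 10² × (2.326 + 0.842)² / 5² = 80.3, and 80.3 / 0.8 = 100.4.

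**Inputs from the plan.** Total dose (mg) = prepregnancy weight × (15 − Hb) × 2.4 + 500. Daily cap = the smaller of 15 mg/kg and 1000 mg (carboxymaltose) or of 20 mg/kg and 1500 mg (isomaltoside), on current weight. Hb lies within 7-10 g/dL. Visits = total dose / cap, rounded up. The caps are used as written, without judging them.

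**Assumptions, not in the documents.** Prepregnancy weight is normal with mean 65 or 75 kg and SD 12; current weight is 8 kg higher; Hb is uniform on 7-10, or normal 9 (SD 0.7) truncated to 7-10. Cost is in units of the price of 100 mg of carboxymaltose: (dose/100) × price ratio + visit cost × visits. Tests are at 0.05, including Shapiro-Wilk, for which the plan gives no level. Each scenario has 600 simulated trials of 100 per arm (standard error at most √(0.25/600) = 2 points).

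**Step 1: two women by hand.**
- 75 kg, Hb 9: 75 × 6 × 2.4 + 500 = 1580 mg. Caps are 1000 and 1500 mg, so two visits on either drug.
- 65 kg, Hb 10: 65 × 5 × 2.4 + 500 = 1280 mg. Caps are 1000 mg and 20 × 73 = 1460 mg, so two visits on carboxymaltose and one on isomaltoside.

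**Step 2: visits at mean weight 65 kg.** The median is 2 in both arms. The means are 2.02 against 1.76 (uniform Hb) and 2.01 against 1.69 (truncated normal Hb). That is 13-16% fewer visits with isomaltoside, because 23-31% of those women need only one.

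**Step 3: how often costs fail Shapiro-Wilk in at least one IV arm (equal prices, four weight and Hb scenarios).**

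| Visit cost | Failure |
|---|---|
| 0 (not counted) | 27-46% |
| 0.5 | 36-56% |
| 1 | 58-69% |
| 2 | 83-99% |
| 4 | 98-100% |
| 8 | 100% |

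Right-skewed weights raise failure to 91-100%, even with cheap visits.

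**Step 4: carboxymaltose (C) against isomaltoside (I).** Price ratio is I/C per mg.

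| Weight, Hb | Price ratio | Visit cost | Mean C / I | Difference | Median C / I | Welch t | Mann-Whitney |
|---|---|---|---|---|---|---|---|
| 75, uniform | 1.0 | 8 | 33.5 / 31.3 | −6.5% | 32.5 / 32.5 | 95% | 10% |
| 75, truncated normal | 1.0 | 8 | 32.3 / 30.2 | −6.4% | 31.9 / 31.9 | 97% | 15% |
| 65, uniform | 1.0 | 8 | 31.3 / 29.3 | −6.6% | 31.0 / 31.0 | 97% | 30% |
| 65, truncated normal | 1.0 | 8 | 30.6 / 28.1 | −8.2% | 30.4 / 29.7 | 100% | 72% |
| 65, uniform | 1.0 | 2 | 19.2 / 18.7 | −2.7% | 19.0 / 19.0 | 27% | 20% |
| 65, uniform | 1.0 | 0.5 | 16.2 / 16.0 | −0.8% | 16.0 / 16.0 | 6% | 5% |
| 75, uniform | 1.1 | 8 | 33.5 / 33.0 | −1.5% | 32.5 / 34.2 | 12% | 74% |
| 65, uniform | 1.15 | 2 | 19.2 / 21.0 | +9.2% | 19.0 / 21.3 | 99% | 98% |

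Other weight and Hb shapes around 75 kg, at equal prices and visit cost 8, gave 98% against 22-27%.

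The loss has a simple cause. Women who need one isomaltoside visit are those with small doses, who already rank among the cheapest. Saving them a visit lowers the mean but changes few rank comparisons. In the 10% dearer row, isomaltoside is slightly cheaper on average, yet its median is higher and Mann-Whitney usually rejects.

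**The case against.** The strongest reply is that the harm depends on prices the documents do not supply, and that they do not say whether visits count as cost at all. If only drug is counted, both IV arms share one dose formula and any gap is a price per mg; at a ratio of 1.15 or more with cheap visits, both tests have 98-100% power. With equal prices and cheap visits both have little power, for a difference of about 1%. This stands, and it limits the point.

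It is also fair that Mann-Whitney on infusion counts alone detects the difference in essentially every simulated trial. The plan's range and quartiles would also show something: the minimum is one visit against two, and at 65 kg with truncated normal Hb the lower quartile is 1 against 2. So the plan would not hide the difference in visits.

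A reader might infer that costs are bound to fail the normality check, for instance because the oral course is fixed and nearly constant in cost. The oral arm does not settle the comparison between the IV arms, where dose varies continuously and failure can be as low as about 30%. A reader might also infer that the plan will miss a real cost difference. It can, under some prices; the documents do not show that it will.

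None of this supplies the missing mean difference and interval once the non-normal branch is taken.

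**Conclusion.** The point holds as a conditional one. If costs fail Shapiro-Wilk, the stated rule yields no mean cost difference and no interval, whatever the prices. That follows from the text alone. How likely failure is, and whether the test result misleads, rests on the assumed weights, Hb distribution, prices and visit costs. The effect ranges from none (a clear price gap with cheap visits) to a 6-7% mean difference found in about 95-98% of trials by comparing means but in 10-15% by Mann-Whitney (equal prices, expensive visits, mean weight 75 kg). With isomaltoside 10% dearer per mg and expensive visits, medians can point the opposite way to means.

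This is a cheap improvement to a secondary outcome. It does not touch the fatigue analysis or the sample size.

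**What to change.** Add to Statistical analysis that costs are exempt from the normality rule. Report the arithmetic mean cost per randomised woman in each arm, and pairwise mean differences with bootstrap (or Welch) 95% confidence intervals; give medians and quartiles as description only. In the outcome definition, state that cost counts drug plus each infusion visit actually made, and list the unit prices used.

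The burden is small: infusion counts and unit prices have to be compiled, and one bootstrap run is added. No dose, cap or visit schedule changes.
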